7.4 Primary Intervention Period

Following the Baseline Visit, all patients will begin their 12-week physiotherapy (or no-physiotherapy) regimen according to their randomisation.

During this period:

- All patients will participate in the Remote Gait Monitoring 1 and Visits 1-3 (Sections 7.3.1, 7.3.2, 7.3.3).
- Patients on the Conventional Physiotherapy arm, if they have access to it will start or continue their conventional physiotherapy and will keep track of it using the Conventional Physiotherapy Tracking Sheet (Appendix F). Patients who did not have access to CPt at the time of inclusion but manage to arrange one during the Primary Intervention Period will restart their PIP.
- On the other arm patients will start the FeetMe rehabilitation program (Section 4.4, Appendix A and B).
- In addition, all patients will keep a falls diary (Appendix G).

7.4.1 Remote Gait Monitoring 1

At the end of the Baseline Visit, all patients will take the FeetMe Insoles, mobile devices and chargers with them to their homes. A Patient User Guide will be provided.

- All patients will use the insoles remotely while performing their day-to-day activities (including physiotherapy) for two weeks. Data will be recorded in standalone mode (without a phone).
- Patients will download the data from the insoles at the end of each day.

7.4.2 Visits 1 and 2

Four and eight weeks after Baseline Visit, two remote visits (Visit 1 and 2) will take place. Patients will be asked to fill in the following questionnaires:

- PDSS-2
- Pain VAS
- Parkinson Disease Questionnaire, Short Form (PDQ-8).

7.4.3 Visit 3

Twelve weeks after Baseline Visit, that is, at the end of the 12-week Primary Intervention Period, all patients will participate in an in-clinic visit (Visit 3), where they will perform the same series of assessments as in the Baseline Visit. Patients will need to bring their FeetMe devices, their diaries, trackers and filled-in questionnaires to the visit.

The following assessments will be performed at Visit 3:

- Gait Assessments, which must be performed in the ON-phase:
 - 6 Minutes Walk Tests (6MWT)
 - Mini-BESTest.

During the 6MWT and the Mini-BESTest patients must wear the insoles. Specific instructions set out in the Site User Manual must be followed when setting up and executing the assessments.

- Disease specific rating scales:
 - MDS-UPDRS
- Other Assessments:
 - FOG-Q
 - PDSS2
 - Pain VAS
 - PDQ39
 - Clinical Global Impression of Improvement / Patient Global Impression of Improvement (CGI/PGI-I)
- Potential adverse events and change in concomitant medication since the last contact.
- The source documents must be collected from the patients and the diary and tracker transcribed into the database.
- Also, the patients further allocation is to be decided (Section 7.4).
- At the end of the visit the patients will return home with their devices (as applicable based on their new or unchanged treatment) and proceed into the Remote Gait Monitoring 2 (Section 7.4.1).

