6 INVESTIGATIONAL PLAN

6.1 Study design and rationale

This is a multicentre, controlled, randomised in two parallel groups, open label study. The study will enroll 150 patients over approximately 18 months and 6 investigational sites.

Having multiple centres enrolling patients will not only maximise the capacity of recruitment but will allow for the evaluation of differences represented by geographical imbalances in the physiotherapy practices across France.

Patients who are found eligible and consent to participate will be randomised either on the conventional physiotherapy or on the FeetMe arm in a 1:1 ratio. Due to the set-up of the FeetMe program (i.e.: personal follow-up of the patients by an APA and the difference in the device needs between the two groups) and the obvious difference in the treatments, a blinded design is not possible. Nevertheless, the objective nature of the primary and main secondary endpoints measured by digital technology and the patient reported nature of most of the remaining outcome measures minimise any potential biassing effect originating from the open label design. Additionally, the final analysis will be performed by a independent blinded statistician.

The equal allocation of patients is maintained during the Primary Intervention Period (from the Baseline Visit till Visit 3) up to the primary endpoint evaluation at Week 12. It is in line with the duration of the FeetMe rehabilitation program. The program is built based on several regulatory recommendation including the HAS and the WHO and expert opinions suggesting that rehabilitation trainings typically show benefit after ten weeks. Additionally, most of the published data supports this duration together with the list of interventions analysed in the European Physiotherapy Guideline for Parkinson's Disease (Keus et al, 2014) where the median duration of the programs is eight weeks. The timing of the primary endpoint at Week 12 is adopted to this standard duration of an intensive rehabilitation therapy off approximately 3 months.

After the Primary Intervention Period patients will be offered to chose how to proceed i.e.: to continue on their original allocation, to switch arms or to stop treatment. In any case the patients will remain in the study until the week 26 EOS visit. The number of patients on the arms at this point will not be controlled and the data gathered will be exploratory in nature. This design is expected to:

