6.2 Schedule of Assessments

Table 6.1 Schedule of Assessments

CIP Number 2023-A00150-45 Final version 0.2

CONFIDENTIAL May 2023

			Primary Inter	vention Period		Long Term Intervention Period			
Visit	Screening ¹	Baseline ²	Visit 1	Visit 2	Visit 3	Visit 1.2	Visit 2.2	Visit 4	End of Study Visit
Timepoint	Day 1	Day 1	Week 4	Week 8	Week 12	Week 16	Week 20	Week 24	Week 26
Visit Window	NA	NA	\pm 7 days	\pm 7 days	\pm 7 days	\pm 7 days	\pm 7 days	\pm 7 days	\pm 7 days
Assessments	In-Clinic + Remote	In-Clinic	Remote	Remote	In-Clinic	Remote	Remote	In-Clinic	Remote
						patients	who switch		
ICF	•								
Eligibility Check	•								
Modified Hoehn and Yahr staging	•							•	
MoCA	•								
Medical History & Demographics		•							
Randomisation	•								
Prior Rehabilitation History	•								
Prior- and Concomitant Medication	•			-	•				
6MWT ³		•			•			•	
Ecological remote gait data collection		for 2 weeks after BL			for 2 weeks after V3			for 2 weeks after V4	
Mini-BESTest		•			•			•	
MDS-UPDRS		•			•			•	

CIP Number 2023-A00150-45 Final version 0.2

CONFIDENTIAL May 2023

FOG-Q	•			•			•	
PDSS-2	•	•	•	•	•	•	•	
Pain VAS	•	•	•	•	•	•	•	
PDQ-39	•			•			•	
PDQ-8		•	•		•	•		
CGI-S / PGI-S	•							
CGI-I / PGI-I				•			•	
Satisfaction Questionnaire	•			•			•	
Falls diary								
Conventional Physiotherapy tracking		From ICF to EOS						
AEs								
Adherence				•			•	

ICF: Informed Consent Form; 6MWT: 6 Minutes Walk Test; Mini-BESTest: Mini Balance Evaluation Systems Test; MOCA: Montreal Cognitive Assessment; AEs: Adverse Events; FOG-Q: Freezing of Gait Questionnaire; MDS-UPDRS I, II & III: Unified Parkinson's Disease Rating Scale parts I, II and III; PDQ-39: Parkinson Disease Questionnaire; PDQ-8: Parkinson Disease Questionnaire Short Form; CGI-S/PGI-S: Clinical/Patient Global Impression of Severity; CGI-I/PGI-I: Clinical/Patient Global Impression of Improvement; PDSS-2: Parkinson Disease Sleep Scale 2;

¹A reflection period of fifteen to thirty days must be given to the subject to decide upon their participation.

² BL assessments will take place right after the Screening Visit.

³ Patients on the FeetMe arm will perform weekly 6MWTs as part of their rehabilitation program using the FeetMe Rehabilitation application.

Note: Visit windows are to be calculated compared to the original schedule, not the previous visit

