7.3 Baseline Visit

All randomised patients will participate in the Baseline Visit. This visit will be on the same day as the Screening Visit.

Patients will be instructed in the use of the FeetMe Monitor and wear the insoles for the duration of the visit, while performing a series of assessments.

The following assessments will be performed at the Baseline Visit:

CIP Number 2023-A00150-45 Final version 0.2

- Demographic data collection (month and year of birth; gender, weight, height, leg length, shoe size)
- Recording of relevant medical history, prior medications
- Gait Assessments, which must be performed in ON-phase:
 - 6 Minutes Walk Tests (6MWT)
 - Mini-BESTest

During the 6MWT and the Mini-BEST gait data will be recorded using the FeetMe Rehabilitation or Evaluation application. Specific instructions set out in the Site User Manual must be followed when setting up and executing the assessments.

- Disease specific rating scales:
 - The Movement Disorder Society sponsored Revision of the Unified Parkinson's Disease Rating Scale (MDS-UPDRS)
- Other Assessments:
 - Freezing of Gait Questionnaire (FOG-Q)
 - Parkinson Disease Sleep Scale 2 (PDSS2)
 - Pain VAS
 - Parkinson Disease Questionnaire (PDQ39)
 - Patient Global Impression of Severity (PGI-S)
 - Clinical Global Impression of Severity (CGI-S)

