8 STUDY ASSESSMENTS

8.1 Gait Assessments

8.1.1 6 Minutes Walk Test (6MWT)

The 6 Minutes Walk Test is a standard performance exercise test designed to assess the functional capacity and walking endurance of a patient in the clinical setting (American Thoracic Society, 2002). The 6MWT consists of a single activity, administered by the Investigator, in a flat indoor corridor at least 30 metres in length, marked every three metres and delimited by cones indicating turnaround points. During the 6MWTs the patients should be in ON state. They will be wearing the insoles. The test will be recorded using a FeetMe application.

The Investigator instructs the patient to walk at a comfortable pace and cover the longest distance possible, then measures the total distance the subject can travel over a six minute period. The total score is the walked distance in metres. This test can be administered by the Investigator or by health care personnel trained in the procedures of the evaluation. The 6MWT takes approximately 10 minutes to complete. The date and time of the assessment are to be recorded in the eCRF.

The standard 6MWT will be performed during the on site visits at BL, Visit 3 and Visit 4. Detailed instructions on how to execute the test are given in the Site User Manual.

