9.2.1 Estimands for primary and key secondary objectives

The main treatment policy estimands for the primary and key secondary objectives of this study, are defined in Table 9.2 below. This table describes the four attributes of target population, endpoint, strategy for addressing intercurrent events, and population-level summary for the endpoints (ICH E9 (R1)).

Target population	Endpoint	Strategy for addressing intercurrent events	Population-level summary				
Primary object	Primary objective in line with H0_1_Primary						
Idiopathic Parkinson'sChange baselinefrom to 		All available data to be included. This is in alignment with the FAS definition. If a patient has a fall up to week 12 and has available week 12 gait data, then the week 12 data will be used and the fall ignored. If the week 12 measurement is not available, whatever the reason (death or injury) the baseline data are used (the patient is not excluded).	In Idiopathic PD patients on CPt, what is the change in gait velocity 12 weeks after randomisation, assessed during the 6MWT, between Conventional Physiotherapy and FeetMe Rehabilitation and whilst the patient is on treatment?				
Key secondary	objective in line w	ith H0_2_KeySecondary					
Idiopathic Parkinson's Disease (PD) patients on Conventional Physiotherapy (CPt)	Change from baseline to Week 12 in stance time variability (ms) assessed during the 6MWT.	All available data to be included. This is in alignment with the FAS definition. If a patient has a fall up to week 12 and has available week 12 gait data, then the week 12 data will be used and the fall ignored. If the week 12 measurement is not available, whatever the reason (death or injury) the baseline data are used (the patient is not excluded).	In Idiopathic PD patients on CPt what is the change in stance time variability 12 weeks after randomisation, assessed during the 6MWT, between Conventional Physiotherapy and FeetMe Rehabilitation and whilst the patient is on treatment?				

Table 9.2 Treatment policy estimands for the primary and key secondary objectives

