9.5.1 Analysis for the primary endpoint

The primary outcome (the change in the gait velocity between baseline and week 12, assessed during the 6 Minutes Walk-Test) will be estimated and compared between Feetme rehabilitation and conventional physiotherapy groups using the constrained longitudinal data analysis (cLDA) model proposed by Liang and Zeger including centre as random effect and adjusted for the covariable "already in a rehabilitation program" considered as stratification factor in the randomisation. We chose to use cLDA model in view of its potential advantages compared to the conventional ANCOVA model. First, the cLDA model provides more flexibility in handling missing data by including all observed data, which, in general, results in more power when testing treatment differences compared with the longitudinal ANCOVA model. Second, compared with the ANCOVA model, the cLDA model provides more appropriate confidence interval estimates, especially in the context of randomised clinical trials where proper randomisation ensures baseline balance. In the cLDA model, both the baseline and postbaseline values are modelled as dependent variables using a linear mixed model (using an unstructured covariance pattern model), and the true baseline means are constrained to be the same for the 2 treatment groups. The between-group mean differences in 12-week change in gait velocity will be estimated by the time-by-arm interaction as treatment effect size. The assumptions of the cLDA model will be checked. We will use the analysis of cDLA model residuals by examining graphically the normality of residuals (histogram and Quantile-quantile plot) and by using the Shapiro Wilk test. In case of strong departure from the normality assumptions (even after applying a logarithmic transformation), nonparametric analysis will be used as recommended by Vickers et al. (reference: 1) Andrew J Vickers. Parametric versus non-parametric statistics in the analysis of randomised trials with non-normally distributed data. BMC Medical Research Methodology 2005, 5:35 2) Conover WJ, Iman RL: Analysis of covariance using the rank transformation. Biometrics 1982, 38:715-724.); absolute changes between baseline and 12-week will be calculated and compared between the 2 treatments groups using nonparametric analysis of covariance adjusted for baseline values. The effect size will be assessed by Hedges's g (standardized differences) computed on rank transformed data with its 95% confidence interval (using the method based on noncentral Student distribution which is a corrected version of Cohen's d taking into account the sample size). A sensitivity analysis will be performed excluding from the FAS population patients who have a change in levodopa medication during the first 3 months. For this sensitivity analysis, we will use the same methodology as that described for the primary analysis.

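### Restarting the primary period for some control patients moves the Week 12 primary assessment in one arm only

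*Protocol*

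**What the plan says.** In section 7.4, the bullet on the conventional physiotherapy (CPt) arm provides that patients without access at inclusion who "manage to arrange one during the Primary Intervention Period will restart their PIP". The bullet on the FeetMe arm contains nothing comparable.

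Five other places fix what the PIP is and when its endpoint is measured:

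- Section 6.1 says that equal allocation is kept "during the Primary Intervention Period (from the Baseline Visit till Visit 3) up to the primary endpoint evaluation at Week 12".
- Section 7.4.3 places Visit 3 as follows: "Twelve weeks after Baseline Visit, that is, at the end of the 12-week Primary Intervention Period, all patients will participate".
- Table 9.2 (section 9.2.1) asks, for the primary estimand, "what is the change in gait velocity 12 weeks after randomisation, assessed during the 6MWT". The key secondary estimand has the same time point, and the strategy is treatment policy using all available data.
- Table 6.1 (section 6.2) sets Visit 3 at Week 12 with a window of 7 days either side, and adds: "Visit windows are to be calculated compared to the original schedule, not the previous visit".
- Section 8.1.1 limits the test that yields both endpoints: "The standard 6MWT will be performed during the on site visits at BL, Visit 3 and Visit 4". Under section 8.1.2, weekly remote 6-minute walk tests (6MWT) are done in the FeetMe arm only.

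Section 4.5 deliberately counts patients with a prescription but no access as part of the control arm.

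**The concern.** The PIP is bounded by visits and ends at the primary assessment, so restarting it naturally means restarting the count to Visit 3. The rule applies in one arm and is triggered by something that happens after randomisation, namely finding a physiotherapist. The time at which gait velocity and stance time variability are measured would then differ systematically between arms, and the Week 12 contrast would no longer be purely the randomised one.

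A statistical analysis plan cannot repair this, because the sentence is an operating instruction to sites. If Visit 3 is moved, a restarting control has no in-clinic 6MWT at the original Week 12 and no remote test to stand in for it. The protocol also does not say whether baseline is repeated after a restart or which measurements then enter the analysis.

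**Working it through.** **Sample size.** The protocol's own figure reproduces and is not affected by this point. With a difference of 14 cm/s, SD 27 cm/s, two-sided alpha 0.05 and 80% power, the normal approximation gives 2 × (1.96 + 0.84)² × 27² / 14² ≈ 58.4, so 59 per group. The t-test gives 59.4, so 60. Allowing for 20% dropout, 60 / 0.80 = 75 per group.

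**Timing.** Inputs: PIP length 12 weeks (section 7.4.3), window ± 1 week (Table 6.1), End of Study at week 26 (Table 6.1), maximum participation 26.5 weeks (Synopsis). Let s be the week after baseline at which the PIP restarts. Baseline is on the day of screening and randomisation. If the restart moves the visits:

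- Visit 3 = 12 + s
- End of Study = 26 + s
- Extra baseline-to-Visit 3 interval, if the original baseline is kept = s / 12

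| s (weeks) | Visit 3 (week) | Extra interval | End of Study (week) |
|---|---|---|---|
| 4 | 16 | 33% | 30 |
| 8 | 20 | 67% | 34 |
| 11 | 23 | 92% | 37 |
| 12 (limit) | 24 | 100% | 38 |

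The permitted window is weeks 11 to 13. A restarted Visit 3 is nominally outside it when 12 + s > 13, that is s > 1. Even if held 7 days early it is outside when 12 + s − 1 > 13, that is s > 2. At the limit s = 12, Visit 3 would fall in the week planned for Visit 4. End of Study passes the 26.5-week maximum once s > 0.5.

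**Which baseline?** The protocol does not say, so both options were followed through. Either way, Visit 3 is not 12 weeks after randomisation, which contradicts Table 9.2.

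- *Original baseline kept.* Visit 3 is no longer twelve weeks after baseline for all patients, against section 7.4.3.
- *New baseline taken.* Section 7.3 says of the Baseline Visit: "This visit will be on the same day as the Screening Visit". A second baseline weeks later contradicts that. It would also be a post-randomisation value, dependent on access, in one arm only. The primary model in section 9.5.1 assumes that "the true baseline means are constrained to be the same for the 2 treatment groups", on the ground that randomisation balances baseline. That ground does not cover a baseline taken after randomisation in selected controls.

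**The case against.** The strongest reply is that only the physiotherapy restarts and the visits stay put. Section 7.4 opens by speaking of a 12-week regimen, the sentence sits beside the tracking-sheet instruction and not in the bullet on visits, and other passages describe all patients attending Visit 3 at twelve weeks and staying until week 26. This reading is possible. But the sentence says that the PIP restarts, although the same section uses the word regimen when it means regimen, and nothing states that visits are held. Even if fixed visits were intended, a site can follow the sentence literally.

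Other points have partial force:

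- The Table 6.1 note mainly guards against drift from one visit to the next, so with a new baseline one could argue that the schedule is re-anchored. The table makes no provision for a second schedule, however, and the conflict with Table 9.2 holds under either baseline.
- Table 9.2 also contains on-treatment wording, which a full course of CPt might seem to serve. That wording does not alter the time point of 12 weeks after randomisation or the all-available-data strategy.
- No passage says that a new baseline would be taken, so that branch is conditional.
- The case s = 12 is a limiting value only, since access must be arranged during the period.
- The number of restarters is unknown and could be small.

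**Conclusion.** The point holds, and the sentence must be corrected before it governs conduct. On its natural reading it makes the timing of the primary and key secondary endpoints depend on arm and on a post-randomisation event, in contradiction to Tables 9.2 and 6.1. It also removes the original Week 12 6MWT for the patients affected.

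The size can be stated for timing only: Visit 3 at week 16 or 20 for a restart at week 4 or 8, approaching week 24 at the extreme, against weeks 11 to 13. This assumes that a restarted PIP carries its visits with it. The protocol gives neither the share of controls who restart nor the effect of a later measurement, so no bias or power figure is attached and the direction is open.

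**What to change.** Replace the restart provision in section 7.4 with a statement that a later start of physiotherapy does not restart the assessment clock: Visit 3 and all Week 12 endpoints are timed from the original baseline in both arms. The later physiotherapy is recorded on the tracking sheet and handled under the existing treatment-policy strategy. This brings section 7.4 into line with sections 6.1 and 7.4.3 and Tables 6.1 and 9.2. It concerns when assessments are made, not when physiotherapy should begin.

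The cost is one protocol sentence and no extra visits. The price is that some controls will have had less than 12 weeks of physiotherapy at Week 12, and the present provision for a full period after access is given up. That sits comfortably with section 4.5, which already keeps patients with no access at all in the arm, although it does not address those who gain access midway. If the sponsor also wants to observe a full 12-week CPt course, an exploratory assessment can be added later, at one in-clinic visit per such patient, provided it does not replace the original Week 12 visit.

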Once the patient has the devices available at their home the rehabilitation program starts with the initial remote training during which the APA specialist explains to the patient the usage of the devices, the safety instructions to follow for ensuring the security of the patient when practising and describes the program, the exercises and how to perform a walking test. Once these first steps are done, the recommended exercises are tested to check if they are well adapted and see if the safety instructions previously described are followed by the patient. During training the patient uses the application on the mobile device. Instructions are given on the screen on how the patient should move reaching a given target. After each exercise a direct biofeedback on the performance is visualised. At the end of the training a specific questionnaire is sent to evaluate the patient's satisfaction regarding the initial training (Appendix C).

Once the program has started regular follow-up calls are scheduled during which the APA specialist discusses with the patients their progress based on the data available in the Mobility Dashboard (e.g.: the patient has difficulties to start his walking with a heel strike) and the feedback of the patient. The calls are conducted in accordance with the Sponsor's internal standard operating procedure. They are initially more frequent (weekly and then bi-weekly). If a patient proceeds up to six months the calls become monthly. During the call a standard set of questions is always asked but the discussion is also adapted to the situation, focusing on motivation, resolving difficulties the patient might face, advising on the movements to be carried out and reviewing the results obtained. Each call is documented in a report and standard data are databased (e.g.: potential adverse events, reason for non-compliance, reported device deficiencies). The reports are also sent to the investigators. If it turns out that an adaptation to the rehabilitation program is needed (e.g. : the patient has difficulties to finish an exercise or/and session or it's easy for the patient to complete all sessions planed in a week) an increase or decrease in the intensity of the program will be applied to match the patient's needs (Appendix B). In addition, if the APA observes that the patient has a low success percentage on an exercise, he will guide them how to improve theresults. All modifications must be validated by the investigator before execution.

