7.5.2 Visits 1.2 and 2.2

Four and eight weeks after Visit 3, that is at week 16 and week 20 from Baseline Visit patients who decided to switch will take part in a virtual remote visit (Visit 1.2 and Visit 2.2 respectively).

Patients will be asked to fill in the following questionnaires:

- PDSS-2
- Pain VAS
- Parkinson Disease Questionnaire, Short Form (PDQ-8).
- 7.5.3 Visit 4

Twelve weeks after Visit 3, that is, at the end of the 12-week Long Term Intervention Period, all patients will participate in an in-clinic visit (Visit 4), where they will perform the same series of assessments as in the Baseline Visit and Visit 3. Patients will need to bring their FeetMe devices, their diaries, trackers and filled-in questionnaires to the visit.

The following assessments will be performed at Visit 4:

- Gait Assessments, which must be performed in the ON-phase:
 - 6 Minutes Walk Tests (6MWT)
 - Mini-BESTest.

During the 6MWT and the Mini-BESTest, patients must wear the insoles. Specific instructions set out in the Site User Manual must be followed when setting up and executing the assessments.

- Disease specific rating scales:
 - MDS-UPDRS
- Other Assessments:
 - FOG-Q
 - PDSS2
 - Pain VAS
 - PDQ39
 - Clinical Global Impression of Improvement / Patient Global Impression of Improvement (CGI/PGI-I)
- Potential adverse events and change in concomitant medication since the last contact.

- The source documents must be collected from the patients and the diary and tracker transcribed into the database.
- At the end of the visit the patients will return home with their devices and proceed into the Remote Gait Monitoring 3 (Section 7.4.4).

7.5.4 Remote Gait Monitoring 3

At the end of Visit 4, all patients will take the FeetMe Insoles with them to their homes. All patients will again use the insoles remotely while performing their day-to-day activities (including physiotherapy) for two weeks. Data will be recorded in standalone mode.

Once the Remote Gait Monitoring 3 period is completed, all patients will return all the FeetMe devices to the site via courier. The site personnel will make sure the data is downloaded as described in the Site User Manual.

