8.7 Falls Diary

Patients have to keep a falls diary throughout their participation in the study by registering falls and near falls, as described in Appendix G. They will need to bring their diaries to the site visits so the data can be registered in the database.

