8.9 Safety Assessments

Adverse events of special interest, serious adverse events and all device related non-serious and serious adverse events will be collected from the signature of the ICF until the participation of the patient is completed within the study. Serious Adverse Device Effects will be reported to the authorities.

In case an adverse event is suspected during the regular follow-up calls between the patient and the APA specialist, the APA specialist will contact the Investigator to enquire the investigation of the event and the assessment of severity and causality.

Detailed instructions on recording and reporting of serious safety incidents will be provided in the Study Procedure Manual.

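### Before Week 12 adverse events are actively sought far more often in the FeetMe arm than in the control arm, because remote Visits 1 and 2 list no adverse-event question

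*Protocol*

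**What the plan says.** Section 8.9 sets one collection period for both arms. Serious adverse events, adverse events of special interest and all device-related events "will be collected from the signature of the ICF until the participation of the patient is completed within the study". Section 8.9.3 counts falls, freezing, dizziness and similar motor events as being of special interest, whether or not they are serious or related.

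The routes by which events come to light differ by arm.

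- **FeetMe arm.** Section 4.4 describes regular calls by the APA specialist: "They are initially more frequent (weekly and then bi-weekly". A standard set of questions is asked, and "Each call is documented in a report and standard data are databased (e.g.: potential adverse events, reason for non-compliance, reported device deficiencies". Investigators receive these reports. Section 8.9 adds a route by which suspected events are passed on to the investigator: "In case an adverse event is suspected during the regular follow-up calls between the patient and the APA specialist, the APA specialist will contact".
- **Control arm.** No such calls are described.
- **Contacts shared by both arms.** At Weeks 4 and 8, section 7.4.2 says "two remote visits (Visit 1 and 2) will take place. Patients will be asked to fill in the following questionnaires", and the list is PDSS-2, pain VAS and PDQ-8. The first visit text to list adverse events is Visit 3 (section 7.4.3): "Potential adverse events and change in concomitant medication since the last contact". All patients keep a falls diary, but section 8.7 says "They will need to bring their diaries to the site visits so the data can be registered in the database", and the first site visit after baseline is also Visit 3.
- **After Week 12.** Under section 7.5.2 only "patients who decided to switch will take part in a virtual remote visit" at Weeks 16 and 20. FeetMe patients who continue have monthly calls (section 4.4).

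**The concern.** Adverse-event counts depend on how often patients are asked. If one arm is asked every week or two and the other once at Week 12, a difference in serious events or events of special interest mixes any true difference with the difference in enquiry. The likely direction is against the FeetMe programme. The opposite problem is that events in controls may be under-reported.

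Timeliness is the second issue. Appendix G defines a type A fall as one with a fracture, internal injury or head injury needing emergency care or admission. A control can enter such a fall in the diary on the day, yet no listed contact brings the entry to the site before Week 12. The sample-size section allows for 5% deaths or injuries by Week 12, which is 0.05 × 150 = 7.5 patients, so such events are expected. Section 10.1 plans no data monitoring committee.

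**Working it through.** The plan gives no figure for the number of enquiries per arm, so there is nothing to reproduce first. The counts below come from the visit texts.

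**Inputs**
- Call frequency: weekly, then bi-weekly (section 4.4). The week of the change is presumably in Figure 2, which is not in the text available, so the number of initial weekly calls, k, is an assumption and is varied from 1 to 12. The value k = 12 is a limiting case with no bi-weekly phase before Week 12.
- Potential adverse events are databased from the calls (section 4.4). That every call asks about them is a close inference from this and from the standard question set.
- Visits 1 and 2: Weeks 4 and 8, no adverse-event item (section 7.4.2).
- Visit 3: Week 12, ± 7 days, adverse-event item present (section 7.4.3, Table 6.1).

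**Method.** List the weeks with a scheduled enquiry from Week 0 to Week 12, counting a call and a visit in the same week once. With gaps g between successive enquiries, an event equally likely at any time in the 12 weeks waits on average Σg² / (2 × 12) weeks for the next enquiry.

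| Arm | Enquiry weeks | Number | Longest gap (weeks) | Mean wait (weeks) |
|---|---|---|---|---|
| Control, as written | 12 | 1 | 12 | 144/24 = 6.0 |
| FeetMe, k = 1 | 1, 3, 5, 7, 9, 11, 12 | 7 | 2 | 22/24 = 0.92 |
| FeetMe, k = 4 | 1, 2, 3, 4, 6, 8, 10, 12 | 8 | 2 | 20/24 = 0.83 |
| FeetMe, k = 8 | 1 to 8, 10, 12 | 10 | 2 | 16/24 = 0.67 |
| FeetMe, k = 12 | 1 to 12 | 12 | 1 | 12/24 = 0.50 |
| Control, enquiry added at Visits 1 and 2 | 4, 8, 12 | 3 | 4 | 48/24 = 2.0 |

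As written, the imbalance is 7–12 to 1. With the visit window the longest control gap is 12 + 1 = 13 weeks. It can be longer for controls who find physiotherapy during the period, because section 7.4 restarts their 12 weeks.

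With the question added, controls have 3 enquiries. The longest gap is 4 weeks on nominal dates, or 4 + 1 + 1 = 6 if one visit is a week early and the next a week late. FeetMe would still have about 7–12, a ratio of 7/3 = 2.3 to 12/3 = 4.

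**The case against.** Several counter-arguments are sound and limit the point.

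- **Collection is continuous.** Section 8.9 runs from consent to the end of participation in both arms, and Table 6.1 appears to show adverse events the same way, although the table is broken in the text available. Controls may report spontaneously at any time, and the Study Procedure Manual, not shown, may add instructions. A reader might infer that sites have no means of acting on a serious fall in a control before Week 12. The documents do not support that. They show only that no active enquiry is listed.
- **The Visit 3 wording.** Asking about events since the last contact suggests that Visit 2 was meant to cover adverse events. If so, section 7.4.2 omits something intended. If not, the look-back read literally starts at Week 8 in controls and leaves the earlier weeks to spontaneous report. Either way the text needs the addition.
- **Falls are recorded prospectively.** Both arms keep a dated diary with severity grades, and the falls endpoint uses it. Fall counts are therefore not subject to 12-week recall, though calls might prompt diary completion in one arm. For falls the issue is mainly late transfer to the site.
- **Little between-arm safety analysis is planned.** The safety objective is exploratory, and section 9.2.7 limits tables and figures to device-related data by default, with all safety data in listings. This reduces the effect on reported comparisons. It does not remove it from the listings, and it does nothing for timeliness.
- **The calls belong to the intervention.** Some asymmetry is unavoidable, which argues for reducing and reporting it.

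A reader might also turn the enquiry ratio into a ratio of event counts. The documents give no rate at which events are captured by frequent calls or by a single late question, so no such figure can be supported.

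**Conclusion.** The point holds as a gap in active enquiry. Up to Week 12, controls have 1 listed adverse-event enquiry against about 7–12 in the FeetMe arm, and a longest gap of 12 weeks against 1–2. The consequence is possible, not certain: a serious event in a control that nobody volunteers can reach the site late, and between-arm readings of serious events and events of special interest partly reflect frequency of enquiry. The primary and key secondary gait endpoints are untouched, and diary-based fall counts are less exposed.

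This rests on three assumptions: that each call covers adverse events, that the number of weekly calls lies within the range shown, and that no document outside the protocol adds control-arm contacts. The size of any bias in event counts cannot be given from the protocol.

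**What to change.** 1. In section 7.4.2 and Table 6.1, add to Visits 1 and 2 in both arms the same scripted adverse-event and serious-adverse-event question, and a read-out of falls-diary entries since the last contact. Handle serious entries at that point under the existing section 8.9.2 procedure.
2. Add an eCRF field for the source of each event: APA call, scheduled visit or spontaneous report.
3. Report all adverse events by arm and by source, and state that enquiry remains more frequent in the FeetMe arm.
4. Do not restrict the between-arm summary to events elicited at scheduled visits while the question covers only the time since the last contact: FeetMe events already given in a call would drop out and that arm would be undercounted. Such a summary works only if the scheduled question covers the whole interval since the previous common visit, whether or not the event was already reported in a call.
5. Optionally, make the same contact at Weeks 16 and 20 for patients who do not switch. The main correction does not depend on it.

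The cost is a few minutes of site time at each of two remote visits that already take place in both arms, and one eCRF field.
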